### **12.2 Response Categories**

#### **12.2.1 Stringent Complete Response (sCR):**

sCR requires, in addition to CR (defined below), *all* of the following:

- Normal free light chain ratio (FLC).
- Absence of clonal cells in bone marrow by immunohistochemistry or immunofluorescence.

#### **12.2.2 Complete Response (CR):**

CR requires *all* of the following:

- Absence of the original monoclonal paraprotein in serum and urine by routine electrophoresis and by immunofixation. The presence of new monoclonal bands consistent with oligoclonal immune reconstitution does not exclude CR.
- Less than 5% plasma cells in a bone marrow aspirate and also on trephine bone biopsy, if biopsy is performed.

- No increase in size or number of lytic bone lesions on radiological investigations (development of a compression fracture does not exclude CR)\*.
- Disappearance of soft tissue plasmacytomas.

\*If not clinically indicated, radiographs are not required to document CR.

Patients in whom some, but not all, the criteria for CR are fulfilled are classified as partial responses (see below), providing the remaining criteria satisfy the requirements for partial response. This includes patients in whom routine electrophoresis is negative but in whom immunofixation has not been performed.

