### 3. PARTICIPANT SELECTION

#### 3.1 Eligibility Criteria

- 3.1.1 Participant must have multiple myeloma and have relapsed following or are refractory to proteasome inhibitors, IMiDs and anti-CD38 mAb therapy
- 3.1.2 Participant must have at least 3 prior lines of therapy
- 3.1.3 Age  $\geq$ 18 years.
- 3.1.4 ECOG performance status  $\leq$ 2
- 3.1.5 Participant must have  $>$  20% plasma cells in the bone marrow core or aspirate differential  $<$ 30 days prior to enrollment.
- 3.1.6 ANC  $>$  1K/uL; Platelets  $>$  50 K/uL without transfusional support
- 3.1.7 Participant must have normal organ function as defined below:
  - total bilirubin  $\leq$ 1.5  $\times$  institutional upper limit of normal
  - AST(SGOT)  $\leq$ 3  $\times$  institutional upper limit of normal
  - ALT(SGPT)  $\leq$ 3  $\times$  institutional upper limit of normal
  - creatinine clearance  $\geq$ 40 mL/min for participants with creatinine levels above institutional normal.
- 3.1.8 The effects of DC/MM fusion and nivolumab on the developing human fetus are unknown. For this reason, women of child-bearing potential and men must agree to use adequate contraception (hormonal or barrier method of birth control; abstinence) prior to study entry and for the duration of study participation. Should a woman become pregnant or suspect she is pregnant while she or her partner is participating in this study, she should inform her treating physician immediately. Men treated or enrolled on this protocol must also agree to use adequate contraception prior to the study, for the duration of study participation, and 5 months after completion of treatment.
- 3.1.9 Ability to understand and the willingness to sign a written informed consent document.

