#### 3.2 Exclusion Criteria

3.2.1 Participants who are receiving any other investigational agents.

3.2.2 Participants with purely non-secretory MM [absence of a monoclonal protein (M protein) in serum as measured by electrophoresis and immunofixation and the absence of Bence-Jones protein in the urine defined by use of conventional electrophoresis and immunofixation techniques and the absence of involved serum free light chain >100 mg/L]. Patients with light chain MM detected in the serum by free light chain assay are eligible.

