#### **12.2.3 Very Good Partial Remission (VGPR):**

VGPR requires, in addition to PR (defined below), all of the following:

- Serum or urine paraprotein detectable by immunofixation but not on electrophoresis. OR
- Greater than or equal to 90% reduction in serum paraprotein plus urine paraprotein <100 mg/24hrs.
- For free light chain only disease, VGPR requires a 90% reduction of involved light chain

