#### **12.2.6 Disease Progression (PD)**

Progression from CR or sCR requires one or more of the following:

- A reappearance of serum monoclonal paraprotein, with a level of at least 0.5 g/dL.
- 24-hour urine protein electrophoresis with at least 200 mg paraprotein/24 hours.
- Abnormal FLC levels of >10 mg/dL, only in patients without measurable paraprotein in the serum and urine.
- At least 10% plasma cells in a bone marrow aspirate or on trephine biopsy.
- Definite increase in the size of existing bone lesions or soft tissue plasmacytomas.
- Development of new bone lesions or soft tissue plasmacytomas.
- Development of hypercalcemia (corrected serum Ca >11.5 mg/dL or >2.8 mmol/L) not attributable to any other cause.

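### For patients measurable outside the marrow only by free light chains, CR in section 12.2.2 requires no light-chain fall, so CR can be assigned, and counted in the ORR, without PR or VGPR being met

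*Combined protocol and SAP*

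**What the plan says.** **Who enters.** Section 3.2.2 excludes purely non-secretory disease. That means no M protein on serum or urine electrophoresis and immunofixation, together with "the absence of involved serum free light chain >100 mg/L". It adds: "Patients with light chain MM detected in the serum by free light chain assay are eligible". A patient negative on every electrophoresis and immunofixation test but with involved FLC above 100 mg/L is therefore admitted. Section 3.1.5 requires more than "20% plasma cells in the bone marrow core or aspirate differential".

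**How response is graded (section 12.2).**
- CR (12.2.2) needs all of four things: "Absence of the original monoclonal paraprotein in serum and urine by routine electrophoresis and by immunofixation"; "Less than 5% plasma cells in a bone marrow aspirate and also on trephine bone biopsy, if biopsy is performed"; no growth in lytic lesions; and plasmacytomas gone.
- sCR (12.2.1) adds a normal FLC ratio and no clonal marrow cells to CR.
- VGPR (12.2.3) is defined on top of PR: "For free light chain only disease, VGPR requires a 90% reduction of involved light chain".
- PR (12.2.4), where FLC is the only measurable parameter outside the marrow, needs a fall of at least 50% in the involved-minus-uninvolved difference, or 50% falls in both the involved FLC and the ratio.

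**How progression is graded.** From CR or sCR (12.2.6), one criterion is enough, and one of them is "Abnormal FLC levels of >10 mg/dL, only in patients without measurable paraprotein in the serum and urine". For patients not in CR (12.2.7), the FLC criterion is an increase of more than 10 mg/dL in the difference.

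**Where these are used.** Section 1.3.2 names CR, VGPR and PR percentages and PFS as secondary endpoints. Section 14.1 gives ORR an exact binomial test.

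**The concern.** FLC is required above CR (sCR) and below it (VGPR, PR), but not at CR itself. In a patient whose disease outside the marrow shows only on the FLC assay, the first CR condition is already met at entry. The better category can then be easier to reach than the lesser ones, and a patient whose light chains have barely moved can count as a complete responder in a formally tested ORR.

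The 12.2.6 criterion adds a second difficulty. Its 10 mg/dL equals the 100 mg/L in section 3.2.2, and it is worded as a level rather than a rise. Two readers could record the same patient as a CR or as a PFS event.

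**Working it through.** **1. The plan's own figure.** Section 14.1 gives n=25, null ORR 0.15, alternative 0.35, one-sided 10% and 82% power. With X binomial:
- P(X≥6 | 0.15) = 0.1615, above 0.10.
- P(X≥7 | 0.15) = 0.0695, so the cutoff is 7 of 25.
- P(X≥7 | 0.35) = 0.8266, which agrees with the stated 82%.

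The power statement is sound. One responder is 1/25 = 4 points, and the test's result changes between 6 and 7 responders.

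**2. Units.** 100 mg/L = 10 mg/dL, so the FLC level that admits these patients is the level in 12.2.6.

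**3. The rules applied to hypothetical FLC-only patients.** Assumptions: electrophoresis and immunofixation negative throughout, no plasmacytoma at baseline, no lytic increase, marrow falling from 25% to 3%, uninvolved FLC fixed at 10 mg/L (so the ratio falls in proportion to the involved FLC). With d = involved − uninvolved:
- PR: (d0 − d1)/d0 ≥ 50%, or involved FLC and ratio both down 50%.
- VGPR: PR, and involved FLC down 90%.
- CR: marrow below 5%, the other three conditions being met already.
- 12.2.6 FLC criterion read as a bare level: involved FLC above 10 mg/dL.

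| Involved FLC, mg/L | Fall in involved | Fall in d | PR | VGPR | CR | FLC level, mg/dL | Above 10? |
|---|---|---|---|---|---|---|---|
| 400 to 400 | 0% | 0/390 = 0% | no | no | yes | 40 | yes |
| 400 to 280 | 30% | 120/390 = 30.8% | no | no | yes | 28 | yes |
| 150 to 105 | 30% | 45/140 = 32.1% | no | no | yes | 10.5 | yes |
| 101 to 70.7 | 30% | 30.3/91 = 33.3% | no | no | yes | 7.07 | no |
| 400 to 160 | 60% | 240/390 = 61.5% | yes | no | yes | 16 | yes |
| 1500 to 150 | 90% | 1350/1490 = 90.6% | yes | yes | yes | 15 | yes |
| 400 to 40 | 90% | 360/390 = 92.3% | yes | yes | yes | 4 | no |

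The first four rows are CR without PR. Rows five and six show that a PR-level or even VGPR-level fall can still leave FLC above the 12.2.6 level.

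**4. Whether another PR route restores the order.** The marrow route in 12.2.4 applies only when marrow is the sole measurable parameter and baseline is at least 30%, so it is closed while FLC is measurable. The plasmacytoma route does restore it for a patient with a plasmacytoma at baseline, because its disappearance is also a 50% reduction. CR without PR therefore needs no baseline plasmacytoma.

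**5. The same values outside CR.** For 400 to 280 mg/L, d falls from 39 to 27 mg/dL. Under 12.2.7 that is not progression on FLC. Without the CR label this patient would have stable disease. With it, the patient is a complete responder, and on a literal reading of 12.2.6 has progressed.

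**The case against.** **The external criteria govern.** Section 12.1 evaluates disease status on the International Uniform Response Criteria, section 14.1 assesses ORR per IMWG, and section 5.14 ties off-treatment to progression by IMWG rather than to 12.2.6. Whether those criteria close the gap cannot be checked from the documents. This limits the claim to the printed text, but it does not remove a printed rule that a reader of section 12.2 would apply.

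**CR and progression on one result.** A reader might infer that the plan necessarily classes a patient as CR and progressed at the same visit, making the PFS date and off-treatment status arbitrary. The documents do not support that as fact. Section 12.1 makes classification at progression relative to best response since entry, and 12.2.6 concerns progression from CR. Read together, they point to a later change from an established CR. The FLC bullet is nevertheless worded as a level, so an ambiguity stands.

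**CR is not automatic.** Marrow must fall from above 20% to below 5%, and the lesion and plasmacytoma conditions still apply. A light-chain patient who is immunofixation-positive at entry must become negative. All of this stands and confines the point to the subgroup described.

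**Placing the normal ratio at sCR may be deliberate.** That is a fair reading of 12.2.1. It does not explain why CR should ask for less FLC fall than PR.

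**Consequence.** The primary endpoint (1.2.1, 14.1.1) is immunologic, section 14 specifies no PFS analysis, and section 14.1 reports no PR or better in the earlier phase I trial in relapsed disease. The number affected may be zero.

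**Conclusion.** The point holds for the printed definitions and for one subgroup: patients negative on electrophoresis and immunofixation, with involved FLC above 100 mg/L and no baseline plasmacytoma. Such a patient can be classed CR, and counted in the ORR, with no PR-level fall in FLC. That 12.2.6 would also call the patient progressed on an unchanged or falling FLC is one available reading, not the only one.

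The size cannot be computed. The documents give neither the share of FLC-only patients nor how often marrow clears while FLC stays high. Assuming a share of 5% to 20%, 0.05 × 25 = 1.25 to 0.20 × 25 = 5 patients would be in the subgroup. A reader might take that as a count of misclassified patients, but it counts only those to whom the gap could apply; the number misclassified is probably small. One such patient is worth 4 points of ORR and matters to the test only when the count lies at the boundary of 6 or 7. The secondary response rates, and possibly PFS, are exposed; the primary endpoint is not. It is worth correcting before responses are adjudicated.

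**What to change.** Confine the change to FLC-only disease.

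1. **12.2.2:** where FLC is the only measurable parameter outside the marrow, add an FLC condition to CR, such as a normal FLC ratio or at least the 12.2.3 reduction with PR met. The second nests CR within PR and VGPR directly. A normal ratio alone could arise partly from a rise in the uninvolved chain, so if it is chosen, the text should also say that PR and VGPR must be met.
2. **12.2.6:** word the FLC criterion as a change after an established CR, consistent with 12.1. The 1500 to 150 mg/L case shows why item 1 is not enough: it satisfies the 90% rule and still lies above 10 mg/dL.
3. **Consistency:** reconcile section 12.2 with the criteria cited in 12.1, 5.14 and 14.1, and state which governs. This concerns endpoint classification; no treatment rule is proposed.
4. **Data:** the section 11 calendar collects the FLC ratio on day 1 of each cycle, in follow-up and at progression, but the lists in 5.11.1 and 5.11.2 omit FLC. Align them, and record the levels behind the ratio, which PR and VGPR already need.

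Do not require PR for CR in all patients. Someone measurable only by marrow with a baseline between 20% and 30% cannot meet the marrow route to PR, so CR would be out of reach. A statement that VGPR requires PR is unnecessary, since 12.2.3 already says so.

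The cost is protocol wording and no new test beyond the calendar. The reported CR rate or ORR may be slightly lower.

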#### **12.2.3 Very Good Partial Remission (VGPR):**

VGPR requires, in addition to PR (defined below), all of the following:

- Serum or urine paraprotein detectable by immunofixation but not on electrophoresis. OR
- Greater than or equal to 90% reduction in serum paraprotein plus urine paraprotein <100 mg/24hrs.
- For free light chain only disease, VGPR requires a 90% reduction of involved light chain

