#### **1.3.2 Secondary Clinical Endpoints**

To determine the clinical response and safety of nivolumab and the DC/MM fusion vaccine in patients with relapsed disease. The percentage of patients achieving complete, very good partial and partial response will be quantified. Minimal residual disease (MRD) status will be determined. Progression free survival (PFS) will be assessed.

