#### **12.2.4 Partial Response (PR)**

PR requires one of the following:

- Greater than or equal to 50% reduction in the level of the serum monoclonal paraprotein and reduction in 24 hour urinary monoclonal paraprotein either by greater than or equal to 90% or to <200 mg/24 hours in light chain disease.
- If the only measurable non-bone marrow parameter is FLC, greater than or equal to 50% reduction in the difference between involved and uninvolved FLC levels or a 50% decrease in level of involved FLC with 50% decrease in ratio,
- If the bone marrow is the only measurable parameter, greater than or equal to 50% reduction in bone marrow plasma cells given that the baseline count was greater or equal to 30%,
- Greater than or equal to 50% reduction in the size of soft tissue plasmacytomas if present at baseline (by radiography or clinical examination).

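### Read literally, the first VGPR route in Section 12.2.3 can raise a PR to VGPR on one fluid alone while paraprotein is still visible on electrophoresis in the other

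*Combined protocol and SAP*

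**What the plan says.** Section 1.3.2 makes the response categories a secondary clinical endpoint: "The percentage of patients achieving complete, very good partial and partial response will be quantified".

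Section 12.2.3 opens with "VGPR requires, in addition to PR (defined below), all of the following". Three lines follow:

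- Route 1: "Serum or urine paraprotein detectable by immunofixation but not on electrophoresis. OR"
- Route 2: "Greater than or equal to 90% reduction in serum paraprotein plus urine paraprotein <100 mg/24hrs"
- A line for free-light-chain-only disease, asking for a 90% reduction of the involved light chain.

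The PR gate is in Section 12.2.4: "PR requires one of the following". Its first criterion starts with "Greater than or equal to 50% reduction in the level of the serum monoclonal paraprotein" and joins this to a urine condition (a fall of at least 90%, or to below 200 mg/24 h).

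CR in Section 12.2.2 asks for "Absence of the original monoclonal paraprotein in serum and urine by routine electrophoresis and by immunofixation".

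Section 14.1 says that response follows IMWG criteria and sets a test for ORR. It gives no figure for VGPR.

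**The concern.** Route 2 and the CR definition both demand a result in serum and in urine. Route 1 alone joins the two fluids with *or*. Taken at its word, one immunofixation-only fluid is enough once PR is met, and nothing is asked of the other fluid beyond PR. A serum fall of a little over half could then rank with a 90% fall as a very good response because of a urine finding.

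The list logic is also faulty. The lead-in calls for every item, yet the first two items are joined by OR and the third concerns a different disease type. Applied strictly, the lead-in would hold every patient to the free-light-chain line. The text therefore needs an edit however route 1 is read.

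What is at stake is the split of responders between PR and VGPR. Compared with a both-fluids rule, the literal route 1 can only move patients upward. The trial has one arm, so depth of response is likely to be read against earlier results; Section 2.3 reports 31% VGPR in the sponsor's previous trial. Serum and urine immunofixation are done on day 1 of every cycle and in follow-up whatever electrophoresis shows (Sections 5.6, 5.9, 5.11.1, 5.11.2), so the finding that triggers route 1 is looked for in everyone.

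**Working it through.** **1. The plan's own figure.** The only stated figure for clinical response is the power of the exact binomial ORR test in Section 14.1: n = 25, null 0.15, alternative 0.35, one-sided 10%, power 82%. With X the number of responders, the rule is X ≥ r, with alpha = P(X ≥ r | 25, 0.15) and power = P(X ≥ r | 25, 0.35).

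- r = 6: alpha 0.1615, too large.
- r = 7: alpha 0.0695, power 0.827.

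The stated 82% is reproduced with r = 7. Every VGPR must already be a PR, so a change to route 1 moves nobody into or out of the responder group. The rule, alpha and power are the same before and after.

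**2. Serum side.** Assumed patient: baseline serum paraprotein 4 g/dL; urine 300 mg/24 h falling to 20 mg/24 h and now seen by immunofixation only. The urine fall is (300 − 20)/300 = 93%, so the urine part of PR is met. Serum reduction = 1 − residual/4.

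| Residual serum (g/dL) | Reduction | PR by serum criterion | VGPR, literal *or* | VGPR, both fluids required |
|---|---|---|---|---|
| 3.0 | 25% | no | no | no |
| 2.1 | 47.5% | no | no | no |
| 2.0 | 50% | yes | yes | no |
| 1.0 | 75% | yes | yes | no |
| 0.5 | 87.5% | yes | yes | no |
| 0.4 | 90% | yes | yes | yes, by route 2 |

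The wording decides the category for serum reductions from 50% to just under 90%.

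**3. Urine side.** Assumed patient: serum immunofixation-only; urine 2000 to 180 mg/24 h and still visible on electrophoresis. The fall is (2000 − 180)/2000 = 91%, so PR is met. Literal route 1 gives VGPR through the serum. Route 2 refuses, because 180 is not below 100.

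**4. Size.** One patient in 25 is 1/25 = 4 percentage points. The documents do not say how many patients would show either pattern, so only a range can be given:

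- none affected: 0 points;
- 1 affected: 4 points;
- 3 affected: 12 points;
- every responder affected at the design ORR (0.35 × 25 = 8.75, about 9): 36 points, an arithmetical ceiling and not a forecast.

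At the null ORR there would be about 4 responders (0.15 × 25 = 3.75), so the ceiling falls to 16 points. Section 14.1 also reports no responses in the earlier phase I trial of the vaccine alone. Zero belongs in the range.

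**The case against.** The best defence is that route 1 can be read differently: whatever paraprotein is left, in serum or in urine, is seen only by immunofixation. On that reading a patient with a visible serum spike fails. It is also selective to take *or* strictly while setting aside the lead-in one line above. In addition, Section 14.1 names IMWG criteria and Section 12.1 cites the International Uniform Response Criteria, so assessors may not work from Section 12.2.3 alone. This stands as far as it goes: misscoring is possible, not certain. It does not repair the text, because two assessors could score the same patient differently and the plan does not say which source prevails.

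A reader might infer three stronger things that the documents do not support.

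- *Any large residual spike qualifies.* It does not, because PR comes first. By the serum criterion at least half of the spike must be gone. Only the separate PR line "Greater than or equal to 50% reduction in the size of soft tissue plasmacytomas if present at baseline", which carries no serum condition when read literally, could let a larger spike through. The point does not rest on it.
- *An unchanged urine trace is enough.* The first PR criterion pairs the serum fall with a urine reduction. Unless its closing reference to light chain disease limits that clause, unchanged urine arguably fails PR. The example above therefore uses urine that fell by 93%.
- *The VGPR percentage is inflated by a known amount.* Any such figure needs the number of PRs without a deep response and the share with one immunofixation-only fluid. The documents give neither.

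It is also fair to say that the consequence is limited. No hypothesis test or threshold is attached to VGPR.

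**Conclusion.** Wrong as written. Literal application allows upward misclassification from PR to VGPR in two situations that route 2 would refuse: a serum fall from 50% to just under 90% with immunofixation-only urine, and immunofixation-only serum with urine at or above 100 mg/24 h. The mismatch between lead-in and list is a second fault in the same section.

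The effect is confined to the descriptive VGPR/PR split, at 4 points per affected patient with 25 as the denominator. The number affected is unknown and may be zero. ORR and its test, CR and the primary immunologic endpoint are untouched. The patient values used above are assumptions chosen to show the logic; the limits of 50%, 90% and 100 mg/24 h come from Sections 12.2.3 and 12.2.4.

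**What to change.** Before responses are scored, edit Section 12.2.3 as follows.

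1. Reword route 1 to cover both fluids, for example: *serum and urine both free of paraprotein on electrophoresis, with paraprotein still found by immunofixation in at least one of them*. This asks for a negative electrophoresis in both fluids, not a positive immunofixation in both, so a patient whose urine never carried paraprotein is not shut out.
2. Change the lead-in so that PR plus any one of the listed items is required, and state that the free-light-chain line applies only to free-light-chain-only disease.
3. Keep the immunofixation requirement in route 1. Section 12.2.2 classes electrophoresis-negative patients without immunofixation as partial responses; waiving it would contradict that rule and could raise the VGPR count.
4. Reconcile the section with the IMWG criteria named in Section 14.1, and say which text governs if they differ.

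No new data are needed, since electrophoresis and immunofixation of both fluids are already scheduled. Sample size and the ORR rule stay as they are. The only cost is that the reported VGPR percentage may be slightly lower.
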